For the MPC exercise-enabled mode, there is a model within the controller that takes as an input the aerobic metabolic expenditure in addition to the CGM and meal inputs. The algorithm uses heart rate and accelerometer data collected on the patient's body to calculate metabolic expenditure. The metabolic expenditure then acts on the model for the insulin dynamics, whereby more energy expenditure and longer duration exercise can lead to a more substantial effect of insulin on the CGM (i.e. the CGM will drop more in response to more intense aerobic exercise and with longer duration exercise). In this way, the model within the MPC control algorithm is always aware of exercise as a continuous input to the system and can respond dynamically to short or long, light, moderate, or intense exercise bouts. We expect that the MPC controller will be able to dynamically adapt to either short or long exercise bouts. We also expect the MPC to dynamically adapt to in-home exercise better, which can be more variable than static exercise that is performed within a clinic under controlled conditions.

The MPC algorithm shall be capable of automating the detection of meals and delivering a portion of the meal insulin. If a meal is detected that has not been reported by the user (i.e. meal carbohydrates entered with insulin bolus delivered), this shall be called a *missed meal insulin*. When missed meal insulin is detected by the MPC algorithm, the app shall calculate the amount of meal insulin that will be dosed and deliver that insulin without an announcement to the user.

Statistical methods

The primary study endpoint is percent of time in range defined as glucose measured by Dexcom G6 or G7 in the range of 70-180 mg/dL. The hypothesis to be tested is if the MPC exercise-enabled closed-loop system with missed mealtime insulin algorithm will be non-inferior as compared to the participant's personal closed loop system. As our main approach, we will perform a two-sided Wilcoxon test for the paired differences. This test is widely used and easily interpreted. However, it cannot accommodate missing data or estimate crossover effects, and while we do not anticipate that these will affect our study outcomes, we plan to conduct a supplemental analysis using a linear regression model with bootstrapped standard errors, which do not require distributional assumptions. In resampling for the bootstrap, we will use study subjects as the sampling unit to account for correlation between their repeated observations. The general model is as follows:

$$(1) \quad Y_{ij} = \beta_0 + \beta_1 Trt_j + \beta_2 Seq_i + \beta_3 Period_j$$

In this model, the outcome Y_{ij} is the percent of time with sensed glucose 70-180 mg/dL for person i in observation period j . Trt_j represents the treatment arm (MPC=1, Control IQ=0). Seq_i is an indicator for sequence (AB vs BA) and $Period_j$ indicates when Trt_j occurred in the sequence. The coefficient β_0 represents the mean response for Control IQ, and the coefficient β_1 represents the difference between treatments to be tested. The coefficients β_2 and β_3 , mean differences for sequence or period, are both expected to equal zero; a large effect or significance test with p-value <0.05 will be considered evidence of a carryover effect. Hypothesis tests will be two-sided with type I error set to 0.05. Because statistical tests are specified and prioritized *a priori* and our proposed endpoints are highly related, we will follow recommendations to report p-values and confidence intervals rather than adjust for multiple comparisons.

Model fit and alternatives: Goodness of fit statistics and model fitting diagnostics will be used to assess for influential points and to evaluate alternative model specifications. If needed to compensate for some skew and heteroscedasticity in secondary outcomes, we will use bootstrapped variance estimators and compare these against robust estimates.

Missing data: Our primary approach will include all available data as an intention-to-treat analysis, regardless of whether study subjects completed both arms. An observation will be included if at least 24 hours of data are available. However, we expect very low levels of missingness; in our previous four-arm crossover study, only one subject withdrew before completing at least two arms. Dropped CGM values will be interpolated over short time periods, using capillary values for calibration when available. In the event of $\geq 10\%$ missingness in either subject data or CGM values, we will analyze outcomes under multiple imputation to compensate for potential bias.

Additional considerations for selected secondary endpoints: The coefficient of variation of glucose is non-normal without an obvious probability distribution, so that bootstrapping will be

our primary approach for this endpoint. Data for percent of time with sensed glucose <54 mg/dl may be sparse; if so, we will present counts of events where glucose went below this level, counting as separate events when the time between them is ≥ 30 minutes.

Confidentiality and Protection of Human Participants

RISKS and BENEFITS

Risks: Given pumps and sensors used within automated glucose control systems are imperfect, there is a risk for hyperglycemia and hypoglycemia, which is mitigated by use of CGM alarms, protocols for managing hypoglycemia and hyperglycemia, and remote monitoring of the first 5 participants. A study investigator will be on call at all times.

Rarely, there can be allergic responses to insulin, such as skin redness, hives, itching of the skin, swelling of the mouth, or breathing difficulties. These reactions are considered very unlikely.

The following events have been identified as possible anticipated device-related adverse events of Dexcom G6 sensor insertion and wear:

- Excessive pain or discomfort from either system deployment or during wear period (8 or greater on a 10-point Likert scale)
- Excessive bleeding, defined as requires removal of the device to stop bleeding
- Hematoma, defined as induration at the sensor insertion location (ecchymosis is a known consequence of needle skin puncture or pressure from sensor pod and will not be captured as an AE)
- Edema from sensor and/or adhesive tape that is significant and non-resolving within 48 hours of sensor pod removal
- Erythema from sensor and/or adhesive tape that is significant and non-resolving within 48 hours of sensor pod removal
- Local infection, defined as presence of pus at either sensor wire or sensor pod site
- Sensor or introducer needle fracture during insertion/wear/removal. For this reason, the study investigator will inspect each removed sensor for the possibility of breakage or fracture. Any evidence of sensor breakage will be recorded and reported to FDA and the sensor company.

Benefits: The participant may not directly benefit from being in this study; however, their participation may help to advance automated insulin delivery technology.

COSTS:

If a participant withdraws early from the study, compensation will be given as follows: \$150 for the usual care arm, \$100 for a confirmed download for t:slim or Omnipod 5 pump and Dexcom sensor from the usual care arm and \$350 for the closed-loop arm. If a participant is asked to repeat a study due to technical problems, he/she will receive an additional \$250 for usual care arm with download, \$350 for the closed-loop arm. There is no compensation for the screening visit.

Safety Oversight:

[name] PA-C will be the study Medical Monitor. [name] has no commercial interest in any of the companies which manufacture any of the devices used in this study.

A Data and Safety Monitoring Board (DSMB) will provide safety oversight. The DSMB will meet a minimum of every 3 months. The DSMB will be informed of all cases of severe hypoglycemia and diabetic ketoacidosis irrespective of device relationship, all device-related SAEs, and all UADEs at the time that they occur during the study and will review compiled safety data at periodic intervals. The DSMB also will be informed of any ADEs not meeting criteria for a UADE if the Medical Monitor requests the DSMB review. The DSMB can request modifications to the study protocol or suspension or complete halting of the study if deemed necessary based on the totality of safety data available. Details regarding the DSMB's role are documented in a separate DSMB document.

Data Collection:

Participant privacy will be protected by using a three-digit identifying number to code study documents. All paper source documents will be kept in a locked cabinet for a minimum of five years.

Recording of Data:

Investigators and staff will record data collected during the clinical trial on the CRF's in a secure HIPAA compliant system run by Prelude Dynamics. The CRFs will include:

1. Screening form
2. iPancreas Training
3. Companion Training
4. Day 1 Intervention Period Study Visit
5. Day 7 Intervention Period Study Visit
6. Day 1 Control Period Study Visit
7. Day 7 Control Period Study Visit
8. Phone Update Form
9. Adverse Event form
10. Serious Adverse Event form
11. Concomitant Medications

The Principal Investigators may authorize other personnel to make entries in the CRF. The coded data collected during this study will be used for analysis of the primary and secondary endpoints listed in this protocol. The key to the code for this study will not be stored in the repository and only named study members on this project will have access to the key for this study. Researchers who request data from the repository will not receive any identifiers aside from date and we do not anticipate that the date will allow those researchers to re-identify the data. However, some of the researchers named on this project may use the data from the repository which would mean that the repository data will still be potentially identifiable to those who have access to the key as part of this project. The coded data will also be stored in the OregonAPC repository according to OHSU IRB protocol 19858. During screening, all new participants will sign the consent form to

store their study data in the data repository. The data to be collected includes: 1) glucose sensor data, 2) blood glucose data, 3) insulin data, 4) physical activity data, and 5) food and exercise data. All data, except for blood glucose, is aggregated by the iPancreas app. The blood glucose data is collected through downloading the Contour Next BG meters and exporting data as an excel file. There are no biological specimens collected during this study.

Monitoring Procedures:

This protocol is written in accordance with the principles established by the 18th World Medical Assembly General Assembly (Helsinki, 1964) and amendments and clarifications adopted by the 29th (Tokyo, 1975), 35th (Venice, 1983), 41st (Hong Kong, 1989), 48th (Somerset West, South Africa, 1996), 52nd (Edinburgh, 2000), 53rd (Washington, 2002), 55th (Tokyo, 2004), 59th (Seoul, 2008), and 64th (Brazil, 2013) General Assemblies. The investigator will ensure that the study described in this protocol is conducted in full conformance with those principles, the protocol, current FDA regulations, ICH Good Clinical Practices (GCP) guidelines, Good Laboratory Practices (GLP) guidelines, local ethical and regulatory requirements, including the Federal Food, Drug and Cosmetic Act, U.S. applicable Code of Federal Regulations (title 21), any IEC requirements relative to clinical studies.

Should a conflict arise, the investigator will follow whichever law or guideline affords the greater protection to the individual participant. The investigator will also ensure thorough familiarity with the appropriate use and potential risks of use of the study device, as described in this protocol, prior to the initiation of the study.

Adverse Event Reporting

At all study visits, study staff will determine if any adverse events (AEs) have occurred. Disease related events that are chronic in nature and occur as part of the progression of the diabetes disease state (i.e. diagnoses of retinopathy, nephropathy, and neuropathy) will not be captured as adverse events in this study. Hypo- and hyperglycemia will not be considered AEs unless participant has positive ketones or displays symptoms of hypoglycemia such as: loss of consciousness, slurred speech, hospitalization or EMS services called.

One of the investigators will write up a description of the adverse event/unanticipated problem. All reportable new information (RNI) will be reported to the IRB within five calendar days after the PI learns of the event. RNI is any information that might meet the regulatory definition of an unanticipated problem involving risks to subjects or others or serious or continuing noncompliance that might impact the criteria for IRB approval. The report will be submitted to the IRB by the principal investigator or study coordinator. A summary of all UP's and adverse events, including those that do not meet the requirement for RNI, will be submitted with the continuing review. All AEs will be monitored until adequately resolved or stable. Information regarding AEs that occur during the study will be entered into appropriate CRFs. Such information will include, at a minimum:

- Date of event
- Severity
- Outcome
- Resolution of event

Definition of Adverse Event

An AE is any clinically significant undesirable experience (sign, symptom, illness, or other medical event) meeting the causality definition above that appears or worsens in a participant during a clinical study. A clinically significant event is any event (sign, symptom, lab/imaging abnormality, or diagnosis) that is noteworthy enough to merit documentation in standard medical records (e.g. history and physical, progress notes, clinic visit notes, etc.). Other non-clinically significant events (e.g. colds, minor headaches, etc.) *may* be documented on the comments CRF. Mild hypoglycemia is expected in persons with diabetes using insulin and are typically self-limiting in nature; thus, this will not be captured as an AE. The Medical Monitor will have the final say in determining the causality. Adverse events that continue after the participant's discontinuation or completion of the study will be followed until their medical outcome is determined or until no further change in the condition is expected.

Serious Adverse Events

A serious adverse event (SAE) is defined as any untoward medical occurrence that:

- Results in death
- Is life-threatening; (substantial risk of dying at the time of the adverse event or suspicion that continued use of the device would result in a participant's death)
- Requires inpatient hospitalization or prolongation of existing hospitalization
- Results in persistent or significant disability/incapacity or substantial disruption of the ability to conduct normal life functions
- Requires medical or surgical intervention to prevent permanent impairment or damage

Exceptions to the SAE definition will include the following:

- Elective surgery
- A planned hospitalization for pre-existing condition, without a serious deterioration in health

Any SAE, including death, due to any cause (related or unrelated to the device), that may occur during a clinical study will be reported to the PI and Medical Monitor immediately (within 1 working day of learning of the event).

Severity of Adverse Events

The following definitions may be used to rate severity of AEs:

- **Mild**

Awareness of signs or symptoms, but easily tolerated; are of minor irritant type that is outside the norm for the disease state or subject; causing no loss of time from normal activities; symptoms would not require medication or a medical evaluation; signs and symptoms are transient. Mild hypoglycemia is expected in diabetes and will not be captured as an AE.

***Example:** ketosis not requiring an ER visit.*

- **Moderate**

Discomfort severe enough to cause interference with usual activities, requiring treatment by family member or emergency personnel

Example: infusion site infection requiring antibiotics prescribed at urgent care.

- **Severe**

Incapacitating, causing inability to do work or usual activities; signs and symptoms may be of systemic nature or require medical evaluation and/or treatment at a health care facility

Example: severe hypoglycemia defined as hypoglycemic event resulting in altered consciousness requiring another person to actively administer carbohydrate, glucagon, or other resuscitative actions.

Relationship of Adverse Events to Study or Study Device

The investigator will categorize the relationship of the event to the study or study device as follows:

- **Not Related**

AE is due to an underlying disease state or concomitant medication or therapy not related to the device, disease or study.

- **Unlikely Related**

AE has minimum or no temporal relationship to the study device, disease or study participation and/or a more likely alternative etiology exists.

- **Possibly Related**

AE has a strong temporal relationship to the study device, disease or study procedures and alternative etiology is equally or less likely compared to the potential relationship to the device, disease or study.

- **Probably Related**

AE has a strong temporal relationship to the study device, disease or study and another etiology is unlikely.

- **Definitely Related**

AE has a strong temporal relationship to the study device, study procedures or disease and another etiology does not exist.

Unanticipated Problems

Unanticipated problems, including study, disease or device-related problems will be detected by reviewing descriptions of known or foreseeable adverse events and risks in the IRB-approved research protocol and the current IRB approved consent form, any underlying disease or conditions of the subject experiencing the adverse event, a careful assessment of whether the adverse event is related or possibly related to the subject's participation in the study or if root cause or associations is with study devices.

Unanticipated Adverse Device Effect (UADE)

An unanticipated adverse device effect (UADE) is not expected to occur. An UADE is defined as any serious adverse effect on health or safety or any life-threatening problem or death caused by – or associated with – the device, if that effect, problem, or death was not previously identified in nature, severity, or degree of incidence in the investigational plan (including documents such as the protocol, the informed consent document, other study-related documents), or any other unanticipated serious problem associated with the device that relates to the rights, safety, or welfare of participants.

During the review of a reported SAE, if the PI and Medical Monitor input determines the severity or extent of the event was not cited in this protocol or associated protocol materials, and the event was classified as, ‘possibly related’ to the device, the event will be documented as an UADE. If the event is classified as an UADE, the Investigator must notify the IRB and the FDA within ten (10) working days of the original SAE notification.

If determined that the UADE presents an unreasonable risk to participants, we will terminate all investigations or parts of investigations presenting that risk as soon as possible, but not later than 5 working days after such determination is made and not later than 15 working days after we first receives notice of the original SAE. We will not resume a terminated study without IRB and FDA approval.

Medical Device Reporting (MDR)

A device issue, whether related to a complaint or not, is an allegation from the participant or study personnel regarding an indication of the failure of a device to meet user expectations for quality or performance specifications. Device issues will be recorded onto appropriate CRFs by site personnel. The CGM and Omnipod devices are currently marketed. Therefore, the PI will follow the required reporting regulations to Dexcom or Insulet if an MDR reportable event occurs.

MDR reportable events are events that manufacturers become aware of that reasonably suggest one of their marketed devices may have caused or contributed to a death or serious injury, or has malfunctioned and the malfunction of the device would likely cause or contribute to a death or serious injury if the malfunction were to recur (21 CFR 803.3).

Confidentiality Procedures:

Staff will maintain the confidentiality and security of data collected in this study. Paper files will be stored in locked filing cabinets in restricted access offices at site. After the study, source documents will be maintained at the participating clinical center (or offsite record storage facilities) 2 years after a marketing application is approved for our group's decision support device or discontinuance of pursuit of marketing approval. Electronic data will be stored on encrypted: computers, laptops and study smartphones. Electronic data is stored in OneDrive and on a secure HIPAA compliant system run by Prelude Dynamics. Sites will be invited to upload data using a password protected folder in Microsoft OneDrive. iPancreas data will be housed in a custom cloud database on an OHSU secure server called the GRM (see below). Access to data/specimens is restricted to study personnel. Access to data requires ID/password authentication.

iPancreas Guidance Remote Monitoring (GRM) Cloud Server

All of the data collected will be streamed over the Internet (using secure sockets encryption) to an OHSU secure instance of an AWS cloud storage server every 5 minutes. Authentication between the phone and the AWS server is done using OAuth2. Data transmitted between the phone and the AWS server is encrypted using HTTPS/SSL. The code managing authentication and data transfer is Python version 3.7.0. Data acquired from the app is displayed via a physician web portal. The physician web portal user interface is written in Javascript version 1.8.5. There is no personally identifiable data stored with the data sent to the AWS server. The server shall be capable of receiving the following types of data (1) CGM data, (2) blood glucose and ketone data, (3) insulin dosing data, (4) insulin on board, (5) alerts, (6) exercise data, and (7) settings. All types of data shall be indexed by participant ID and by date/time. Data shall be stored on the server in a secure database. Each data packet shall be accompanied by an authentication identifier determined through OAuth.

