Primary Objective:

- To confirm non-inferiority of the OHSU MPC exercise-enabled closed-loop system with missed mealtime insulin detection algorithm as measured by percent of time 70-180 mg/dL on Dexcom G6 CGM as compared to use of the participant's personal closed loop delivery system.

Secondary Objective:

- To confirm non-inferiority of the OHSU MPC exercise-enabled closed-loop system with missed mealtime insulin detection algorithm as measured by other glucose metrics as compared to use of the participant's personal closed loop delivery system.

Study Hypothesis:

We propose that the use of the OHSU MPC exercise-enabled closed-loop system with missed mealtime insulin detection algorithm will be non-inferior within a time in range margin of 7% as compared to the participant's closed loop delivery system in patients with elevated baseline A1C values.

Endpoints

Primary Endpoint:

- Percent of time with sensed glucose between 70-180 mg/dl across the study duration

Secondary Endpoints:

- Percent of time with sensed glucose between <70 mg/dl across the study duration
- Percent of time with sensed glucose <54 mg/dl across the study duration
- Percent of time with sensed glucose >180 mg/dl across the study duration
- Mean sensed glucose across the study duration
- Coefficient of variation of glucose across the study duration
- Mean amount of insulin delivered per day (in units/kg) across the study duration

Study Type

This is a multi-center, randomized, two treatment, crossover non-inferiority trial designed to compare the glucose control resulting from the use of the OHSU MPC exercise-enabled AP system with missed mealtime insulin detection algorithm (Intervention Period) as compared to usual care using a closed loop insulin delivery system, either the t:slim X2 pump with Control IQ or Omnipod 5 system (Control Period).

Study Population

Study population will be participants with type 1 diabetes, ages 18 years of age and older. Up to 36 participants will be recruited to participate in studies across two sites.

Power Analysis

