A sample of 28 subjects provides at least 80% power for testing our primary endpoint in a non-inferiority framework comparing the exercise-enabled MPC algorithm with missed meal insulin detection to use of participant's personal closed loop system. Assumptions informing this calculation were derived from simulations showing an expected mean percent time in range (70-180 mg/dL) for control IQ that was 3.7% lower (as a difference rather than a ratio) and standard deviations (SDs) for the two conditions of approximately 16 to 19. From this, we assume the SD of the within-subject difference will be approximately 17% and use a one-sided paired t test at the 0.025 level of significance for a mean difference of 3.7% time in range versus 6% as the non-inferiority margin. We plan to recruit up to 36 subjects with goal enrollment of 30 subjects (about 15 at each center).

Protocol Summary:

Participants will undergo one 7-day Intervention Period and one 7-day Control Period in randomized order. During the 7-day intervention study, participants will wear an Omnipod to deliver Fiasp insulin and a Dexcom G6 CGM. The CGM system will provide sensed glucose data every 5 minutes. Sensed glucose data will be wirelessly transmitted via Bluetooth Low Energy (BTLE) from the Dexcom G6 transmitter to the smartphone master controller every five minutes. The smartphone will wirelessly communicate via BTLE to an Omnipod through a Personal Diabetes Manager (Insulet Corp.). The closed-loop system will receive activity data through a Polar M600 watch worn by the participant. Participants will eat one meal in clinic and complete system training on Day 1 and then spend the rest of the 7 days at home. During the 7-day Control Period, the participant will continue their usual diabetes care regimen using a t:slim X2 pump with Control IQ enabled or the Omnipod 5 closed loop system.

Participant Criteria

Inclusion Criteria:

1. Diagnosis of type 1 diabetes mellitus for at least 1 year.
2. Age 18 years and older.
3. Current use of a t:slim X2 insulin pump with the use of Control IQ or the Omnipod 5 system with closed loop enabled with Dexcom G6 or G7 for at least 12 weeks.
4. Willingness to use Fiasp insulin during intervention study
5. Lives with another person age 18 or older who will sleep in the house at night and that can attend the training on using the system.

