17. Chronic usage of any immunosuppressive medication (such as cyclosporine, azathioprine, sirolimus, or tacrolimus).
18. Bleeding disorder, treatment with warfarin, or platelet count below 50,000.
19. Allergy to Fiasp insulin.
20. Current administration of oral or parenteral corticosteroids.
21. Any life-threatening disease, including malignant neoplasms and medical history of malignant neoplasms within the past 5 years prior to screening (except basal and squamous cell skin cancer).
22. Current use of beta blockers or non-dihydropyridine calcium channel blockers.
23. Current use of any medication intended to lower glucose other than insulin (ex. use of metformin or liraglutide) or SGLT-2 inhibitors (for diabetes or other indications, ex. use of empagliflozin or ertugliflozin).
24. Gastroparesis
25. Low carbohydrate diet at the time of screening defined as less than 50 grams of carbohydrate per day.
26. Any clinically significant disease or disorder which in the opinion of the Investigator may jeopardize the participant's safety or compliance with the protocol.

Participant Recruiting:

Participants will be recruited from 2 sites in the United States, one of which will be Oregon Health & Science University (OHSU). Non-English speaking participants will not be recruited since this protocol would require the use of medical devices and mobile software that do not

have non-English versions available. Up to 60 participants may be screened in this study. Goal enrollment is 30 participants across both sites with up to 6 replacements as needed to collect data from 28 participants. However, re-screening is allowed up to one time per individual, no sooner than 2 weeks and no longer than 3 months and after initial screen. It is anticipated that each site will enroll about 15 participants, but this may be adjusted if needed to complete enrollment in a timely fashion.

Withdrawal Criteria

The participant may withdraw at will at any time or at the discretion of the Investigator.

A participant must be withdrawn if the following applies:

- Severe Hypoglycemia during the treatment period (control or intervention period). Severe hypoglycemia is defined as any event that required the assistance of another person to administer carbohydrate, glucagon, or other resuscitative actions.

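### The primary non-inferiority margin is 7 points in the Study Hypothesis but 6 points in the Power Analysis, so the success criterion is not uniquely defined

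*Protocol*

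**What the plan says.** The Study Hypothesis section of the protocol expects the investigational closed-loop system to be "non-inferior within a time in range margin of 7" percent relative to the participant's own closed-loop system.

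The Power Analysis section addresses the same endpoint (percent of time at 70-180 mg/dL) and the same comparison with a different margin. It states: "A sample of 28 subjects provides at least 80% power for testing our primary endpoint in a non-inferiority framework". The planned calculation is a paired t test, one-sided at 0.025, and the expected difference is set "versus 6% as the non-inferiority margin". The expected difference of 3.7 comes from simulations with a time in range "for control IQ that was 3.7% lower (as a difference rather than a ratio"), that is, in favour of the intervention. On variability, "we assume the SD of the within-subject difference will be approximately 17" percent.

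The Statistical methods section says that non-inferiority will be tested, by a Wilcoxon test on the paired differences with a supporting regression, and gives no margin.

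**The concern.** In a non-inferiority trial the margin defines the null hypothesis and so the rule for success. Here two values are on file for one primary test. They are on the same scale: the Power Analysis says its 3.7 is an absolute difference and sets it directly against the 6, and the 7 is described as a margin of time in range. They cannot be read as one quantity expressed in two ways.

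An estimate falling between the two thresholds would count as success under one section and failure under the other. Whichever value was then applied, a reader could ask whether it was chosen with the confidence interval in view. If 6 is the intended margin and 7 is applied, the one-sided 2.5% error rate no longer holds at 6.

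**Working it through.** **Inputs.** All are from the Power Analysis unless noted.
- n = 28
- SD of the within-subject difference = 17
- one-sided alpha = 0.025, paired t test
- true difference = +3.7 (intervention minus control)
- margin M = 6, or 7 from the Study Hypothesis

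**Which margin produced the 28?** Power is P(T > t(0.975, n-1)), where T is noncentral t with n-1 degrees of freedom and noncentrality (M + 3.7)/17 × √n.
- M = 6: noncentrality 9.7/17 × √28 = 3.02, power at 28 = 82.9%. Power is 79.8% at n = 26 and 81.4% at n = 27, so 27 are needed.
- M = 7: noncentrality 10.7/17 × √28 = 3.33, power at 28 = 89.4%; 22 are needed.

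The normal approximation gives 25 and 20. The protocol's 28 with at least 80% power therefore reproduces, and it fits a margin of 6 closely. With 7 it would be six more than required.

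**Where is the pass mark?** The half-width of the 95% confidence interval is t(0.975, 27) × 17/√28 = 2.052 × 3.213 = 6.59. Non-inferiority requires observed difference - 6.59 > -M:
- M = 6: observed difference above 6.59 - 6 = +0.59
- M = 7: observed difference above 6.59 - 7 = -0.41

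**How often would the choice decide the verdict?** Any result that passes at 6 also passes at 7, so the probability of a split verdict is the difference in pass probabilities.

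| True difference | Pass at 6 | Pass at 7 | Split verdict |
|---|---|---|---|
| +3.7 | 82.9% | 89.4% | 6.5% |
| 0 | 43.7% | 55.6% | 11.9% |
| -3.7 | 10.2% | 16.6% | 6.4% |
| -6 | 2.5% | 4.8% | 2.3% |

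In the last row, the pass rate at 7 has noncentrality 1/17 × √28 = 0.31.

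**Sensitivity of the pass marks (6 / 7).**
- n = 30, SD 17: +0.35 / -0.65
- n = 36, SD 17: -0.25 / -1.25
- n = 28, SD 19: +1.37 / +0.37

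The thresholds move, but the one-point gap stays.

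**Effect of the Wilcoxon test.** With normal differences its relative efficiency to the t test is about 0.955, so 28 behave like 28 × 0.955 = 26.7. Power lies between the t-test values at 26 and 27: 79.8% to 81.4% for a margin of 6, and 86.9% to 88.3% for 7.

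**The case against.** - **The 7 could be the real margin and the 6 a cautious planning value.** Only the 7 appears in the formal hypothesis, and planning against a tighter margin is possible. But the protocol does not say so; it calls the 6 the non-inferiority margin outright.
- **A statistical analysis plan may exist and may name the margin.** For that reason the silence of the Statistical methods section carries little weight here. The finding rests on two explicit statements in the protocol, and a plan that adopts one would still contradict the other.
- **The sample size is not harmed.** This stands. On the protocol's t-test assumptions, 28 give at least 80% power under either margin.
- **The 4.8% is an error rate only if 6 is the true margin.** This also stands. If 7 is intended, a 6-point deficit lies inside the margin and the error at -7 is 2.5%. The figure shows the cost of applying 7 when 6 was meant.
- **The thresholds assume exactly 28 analysed.** Participant Recruiting says "Goal enrollment is 30 participants across both sites with up to 6 replacements as needed to collect data from 28 participants", so the final number may differ. The gap does not depend on it.
- **Choosing the margin after the data is only a possibility.** Agreed; nothing in the protocol permits it. A single stated value removes the question.

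**Conclusion.** The contradiction is real and the protocol does not resolve it: the success criterion is stated two ways. The two thresholds lie one percentage point apart. On the planning assumptions (28 analysed, SD 17, paired t interval), the conclusion would turn on the choice of section with probability of about 6.5% at the hoped-for difference and about 12% if the systems are equal. Power is adequate under both margins if the true difference is +3.7 in favour of the intervention, so the problem lies in the decision rule and not in the trial's size. Because the margin is the primary decision rule, it must be corrected before the primary comparison.

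**What to change.** State one margin, in absolute percentage points of time in range and with its justification, in the Study Hypothesis, Power Analysis and Statistical methods sections. The protocol at present justifies neither value.

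- **Adopting 6:** change the single figure in the Study Hypothesis. The sample size and power statement stand as written. The cost is a pass mark one point stricter than the hypothesis now implies.
- **Keeping 7:** change the margin in the Power Analysis, restate power at 28 as about 89%, and justify the wider margin. The at-least-80% statement would remain true.

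Fix the value before any comparison of the two periods, preferably before the safety assessment of the first five participants. That look concerns time below 54, below 70 and above 300 mg/dL and adverse events, and does not test time in range. It does compare the periods on the same sensor data, so settling the margin beforehand prevents any suggestion that it was chosen with data in view. Either route is a short protocol amendment with no change to enrolment.
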